medically/psychiatrically at risk in the judgment of the study physician (or licensed medical professional designated to consult in his absence) or PI; (c) positive urine screen for cocaine, opiates, methadone, benzodiazepines, barbiturates, amphetamines, methamphetamines, or PCP (NOTES: THC will be tested but will not be an exclusionary criterion; participants with valid prescriptions for opiates, benzodiazepines, barbiturates, amphetamines or methadone will not be excluded; participants failing the toxicology screen will be allowed to re-screen once); (d) breath alcohol level > 0.01 (one re-screen allowed); (e) binge alcohol drinking (4/5 [female/male] drinks per day more than 9 days in the past month); (f) systolic/diastolic BP greater than or equal to 160/100, or below 90/50 (one re-screen allowed); (g) heart rate greater than or equal to 105bpm, or below 45bpm (one re-screen allowed); (h) ever used reduced nicotine cigarettes; (i) smoke 'roll your own' cigarettes exclusively, (j) used smoking cessation medications within the past three months, (k) are currently enrolled in a smoking cessation program; (l) actively trying to quit; (m) used other tobacco products (including e-cigarettes) more than 9 days in the following medications:

- Phenytoin [Brand Name: Dilantin]
- Carbamazepine [Brand Name: Tegretol, Carbatrol, Equetro, Epitol]
- Oxcarbazepine [Brand Name: Trileptal]
- Primidone [Brand Name: Mysoline]
- Phenobarbital
- Bendamustine (Treanda)
- Clopidogrel (Plavix)

- Clozapine (Clozaril, FazaClo)
- Erlotinib (Tarceva)
- Flecainide (Tambocor)
- Fluvoxamine (Luvox)
- Irinotecan (Camptosar)
- Olanzapine (Zyprexa)
- Ropinirole (Requip)
- Tacrine (Cognex)
- Theophylline (Theo Dur, etc.)

Measures to assess each of these criteria are described below (see Study 2). If the participant needs to be rescreened, or if their eligibility is pending review by the P.I., Co-I, or LMP, they will be required to attend an additional visit.

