During the baseline session eligibility will be assessed during the following checkpoints: The first checkpoint will be during the physiological measures portion. If the participant fails the breath alcohol test, urine drug screening (minus valid Rx or THC), pregnancy test, or if the blood pressure reading is outside of the permissible range, they will receive \$10. If the participant does not pass the smoking confirmation tests (if $CO \le 8ppm$, and NicAlert Strip ≤ 2), they will be dismissed without payment. While awaiting results for physiological measures, participants may begin completing questionnaires in order to expedite the screening process. The second eligibility checkpoint will be after the participant answers the self-administered forms (Brief Medical History, Prime MD, etc.). If the participant is deemed ineligible at the second eligibility checkpoint they will receive \$15. The third eligibility checkpoint will be after the interviewer administered forms (Timeline Follow-Back, Tobacco Use History Questionnaire, etc.). If the participant is deemed ineligible at this point they will receive the full \$25 for the session.

Intervention Phase. If a participant is deemed to be eligible, they will be distributed a 1-week supply (based on typical # cigarettes/day x 1.5) of NNC (.8 mg nicotine yield) study cigarettes to smoke exclusively during one baseline week. Next, ten participants will be randomly selected to receive the lowest VLNC nicotine dose (.03 mg nicotine yield) each of four pre-quit weeks (immediate reduction), and the remaining ten participants will receive cigarettes containing nicotine yields of .7 mg for week 1, .26 mg for week 2, .12 for week 3, and .03 for week 4 (gradual reduction). Thus, we will assess the feasibility of these tapering regimens in this pilot study. Study cigarettes provided will match participant's preference for menthol or non-menthol, with menthol doses adjusted slightly based on availability. Participants will be strongly

encouraged to smoke the study cigarettes exclusively, and to avoid smoking their usual brand or any NNC cigarettes.

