3) Practicality represents the broadest of the feasibility constructs. This will encompass the degree to which we are able to carry out all the elements of the planned developmental pilot study successfully and efficiently. This includes recruitment, screening, randomization, and treatment components. For these elements of the study, we will record number of attempts, duration, protocol deviations and errors, and suggestions for improvement.

Study 2. Randomized Controlled Trial (Aim 2), Intermediate Outcomes (Aim 3), and Mechanisms (Aim 4)

Study Goals and Overview. The primary goals of Study 2 are to test effects of the targeted intervention developed in Study 1 on smoking cessation (Aim 2) and intermediate outcomes (Aim 3), as well as to explore potential mechanisms that could guide future implantation of this treatment strategy (Aim 4). Approximately 300 treatment-seeking smokers will be screened using similar methods and inclusion/exclusion criteria as in Study 1. The expectation is that 80% of participants (n=208) will be eligible and randomized to one of four conditions (52 per condition) over a 3 year period. The four conditions will comprise a 2 x 2 between-subjects design, with facilitated extinction (targeted) treatment (present vs. absent) crossed with tapering schedule (immediate vs. gradual). As in Study 1, once a participant has been deemed eligible, a baseline week of smoking NNC study cigarettes will be followed by four weeks of smoking VLNC cigarettes, either through immediate or gradual reduction to the lowest level. Five weekly counseling sessions will occur (at the start of each week), and the Target Quit Date will occur one week after the fifth weekly session (+/- 3 days). On the Target Quit Date, participants will attend an additional session, including counseling as well as two tests of intermediate outcomes (cue reactivity and cigarette purchase task). Follow-up visits will occur at 2 and 6 months following the TQD (+/- 7 days). Please see Appendices on pages 33-34 for further details.

Exclusion Criteria: Study 2 exclusion criteria will match those of Study 1, with the following modifications: (a) use of smoking cessation medications will be exclusionary only for the past month and with the exception of sporadic use of NRT for non-cessation purposes, (b) use of

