other tobacco products (including e-cigarettes) will only be exclusionary if participants use them as their primary source for tobacco intake, (c) will limit the number of participants from the same street address to one, and (d) will not include any participants that participated in the precessation Varenicline study conducted at our facility due to the similarity in the protocols. Additionally, eligibility determination may require outside medical clearance, as determined necessary by the LMP, either prior to or after the screening visit.

Recruitment: Recruitment methods will include those used for Study 1, along with the following additions: (1) local fairs/ markets (e.g., USF "Bull Market"), (2) expanded social media platforms to include Reddit, Instagram, and Twitter, and (3) an online research panel (Plaza Research Tampa). Participants recruited through the research panel will receive an email about the study and will undergo a brief online survey and/or telephone pre-screening conducted by the research panel staff, which will include basic eligibility criteria (e.g., age, smoking status, interest in quitting smoking, and specific medical criteria). Additionally, we will establish a study webpage for participants to visit and obtain more information about the clinical trial. The study webpage link will be included within the advertisements. Once directed to this page, participants will have the option to call the study number, send an email, or provide their contact information.

Telephone Screening: Potential participants will be screened via the telephone prior to attending their first visit. In addition to assessing the criteria listed below for Study 2, participants must express interest in quitting within the next 30 days.

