Baseline/Screening Session: Participants who meet study inclusion/exclusion criteria based on telephone/internet screening will be scheduled for a baseline/screening session at the Tobacco Research and Intervention Program (TRIP). Upon arrival for the session, study information will be presented and written informed consent will be obtained prior to any data collection. After consent is obtained, breath testing will occur to verify smoking status (CoVita Micro+ Smokerlyzer® CO meter (Bedfont Instruments) and alcohol abstinence (Intoximeter IV; St. Louis, MO). A urine sample will be collected to assess for psychoactive drug use (Andwin Scientifi 9-Panel Drug Card Test), to further verify smoking status if applicable(CO levels ≤ 8ppm) (i.e., cotinine; NicAlert; Nymox Corp., Hasbrouck Heights, NJ), and to ensure that women are not pregnant via HCG detection (Fisher HealthCare™ Sure-Vue™ Urine hCG Test Kits). Blood pressure and heart rate will be measured using a CritiCare monitor, with manual measurements taken as a back-up if elevations are detected. Next, the following general and smoking-related questionnaires and interviews will be administered, selected according to established psychometric properties and relevance to inclusion/exclusion criteria and study aims:

General: A demographic form and health status questionnaire will collect information on age, gender, race, ethnicity, socioeconomic status, employment, education, marital status, height, weight, current health status, medical history, and current medications. An alcohol use questionnaire will be given to collect alcohol use information over the past month (NIAAA, 2003) as well as a drug use questionnaire that will capture use over the past year. The MINI International Neuropsychiatric Interview (v. 7, 1/5/15; Sheehan et al., 1998) will be administered by trained staff to diagnose DSM-V Axis I disorders (only sections relevant to inclusion/exclusion criteria will be administered). The Prime MD, a brief questionnaire developed for evaluation of mental disorders by primary care physicians (Spitzer et al., 1999), will be administered, as well as the Beck Depression Inventory (BDI; Beck, Ward, & Mendelson, 1961), if applicable, to assess depression in participants who endorse suicidal ideation or Major Depressive Disorder on the Prime MD. Participants will also complete a contact information

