Intervention Phase. As in Study 1, all participants will be given a supply of normal nicotine content (NNC; .8 mg yield) study cigarettes to smoke for a baseline week, based on typical # cigarettes/day x 1.5. However, if a participant normally smokes 120mm cigarettes, then the amount supplied will be determined by multiplying their typical number of cigarettes/day x 2 (because the Spectrum cigarettes are regular length at approximately 80mm). This will introduce participants to the taste and feel of Spectrum research cigarettes, prior to receiving reduced nicotine cigarettes, thereby avoiding the confounding of changing brand and nicotine content simultaneously. Prior to the baseline session, participants will be randomly assigned to one of four treatment conditions, that vary according to a 2 x 2 between subject design: (1) targeted intervention with immediate transition to VLNC cigarettes, (2) targeted intervention with gradual transition to VLNC cigarettes, (3) standard intervention with immediate transition to VLNC cigarettes, (4) standard intervention with gradual transition to VLNC cigarettes. Overall, the intervention phase will consist of six visits, with five of them preceding the TQD which will occur one week after the fifth weekly session. The sixth session will occur on the TQD. At each of the pre-quit visits, participants will (1) receive their supply of study cigarettes for the upcoming week, (2) complete assessments related to compliance and reactions to assigned study cigarettes, (3) answer questions regarding health changes (if any) and date/length of last menstrual period for pre-menopausal women (to assess potential pregnancy), which will be documented on the 'Health Changes Questionnaire' (4) complete a Cigarette Purchase Task for their study and usual brand cigarettes (5) complete the QSU-brief for study and usual brand cigarettes (6) complete a Cigarette Evaluation Scale for the study cigarettes (7) complete the Drug Effects/Liking Scale for their study cigarettes (8) complete the Timeline-Follow Back interview to update their smoking, alcohol, and drug use since the prior visit, and (9) receive brief counseling according to condition. As in Study 1, if the participant's breath alcohol level is > 0.03 the researcher will not start the session.

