detailed screening/baseline session at the Tobacco Research and Intervention Program (TRIP) of the Moffitt Cancer Center. During this session, informed consent will be obtained, followed by administration of questionnaire and interview-based assessments to determine eligibility based on inclusion/exclusion criteria (see below). Eligible participants will receive study cigarettes for five weeks, using either an immediate or gradual tapering regimen. All participants will receive written materials to assist in their quit attempt, as well as in-person smoking cessation counseling. In the RCT only, participants will engage in two intermediate tests of smoking behavior, and will attend follow-up sessions 2- and 6-months following a target quit date (TQD). Participants will be compensated for attendance at treatment and follow-up sessions, for completing workbook assignments and data collection activities, and for their performance on smoking behavior tests. The potential compensation for each participant in the developmental pilot study (Study 1) is \$200, and for the RCT (Study 2) the potential compensation is \$260. The eligibility criteria for both studies are as follows:

Inclusion criteria: (a) \geq 18 years of age; (b) smoke at least 5 cigarettes daily for the past year; (c) expired-air carbon monoxide (CO) > 8 ppm (if \leq 8 ppm, then NicAlert Strip > 2); (d) current motivation to quit smoking; and (e) able to speak and read English sufficiently for completion of consent form and questionnaires.

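### Study 2 assigns treatment before consent and in-person eligibility checks, so discretionary exclusions can follow allocation with the arm not concealed

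*Combined protocol and SAP*

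**What the plan says.** **Timing of assignment.** Study 2, Intervention Phase: "Prior to the baseline session, participants will be randomly assigned to one of four treatment conditions".

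**Timing of consent and eligibility.** Under Baseline/Screening Session, only telephone or internet screening comes before the visit. On arrival, "written informed consent will be obtained prior to any data collection". Breath, urine, blood pressure, heart rate, questionnaire and interview checks come after consent. Section E (Human Subjects Involvement and Characteristics) gives the same order: "During this session, informed consent will be obtained, followed by administration of questionnaire and interview-based assessments to determine eligibility".

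**Later determinations.** The Study 2 Exclusion Criteria add that "eligibility determination may require outside medical clearance, as determined necessary by the LMP, either prior to or after the screening visit". The Study 1 eligibility text, on which Study 2 builds, requires a further visit "if their eligibility is pending review by the P.I., Co-I, or LMP". Participant Compensation pays for such a visit.

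**The overview.** Study Goals and Overview says: "The expectation is that 80% of participants (n=208) will be eligible and randomized to one of four conditions (52 per condition". It also says that "once a participant has been deemed eligible, a baseline week of smoking NNC study cigarettes will be followed by four weeks".

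**What happens to people who fail.** They leave at the checkpoint. For failed smoking confirmation, "they will be dismissed without payment"; other failures receive a partial or full session payment.

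**Blinding.** The last sentence of the Intervention Phase text on interventions says that participants, counsellors and experimenters are blind to assignment. It sits in the sentence on the tapering schedules. No sequence generation, list-holder or concealment method is described.

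**The concern.** The baseline session named in the assignment sentence is the visit at which consent and final eligibility are settled. Read literally, a person has an arm before anyone has confirmed that they may enter the trial. The overview's account of the 208 points the other way, so the two places need reconciling.

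Randomisation protects a comparison only if membership of the compared groups cannot depend on the arm. An exclusion made after allocation by someone who knows the arm can break that protection. Here the opportunity is real but limited. Arm-specific counselling begins at Visit 1, the same visit as the eligibility checks (Intervention Phase; Appendix, procedures by visit). One exclusion criterion also rests on the judgement of the study physician or the PI about medical or psychiatric risk. What is at stake is the targeted-versus-standard effect on abstinence, one of the two main effects that the trial is sized to detect.

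**Working it through.** **1. Order of events, taken from the text.**

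| Step | Where stated | Position |
|---|---|---|
| Telephone/internet screen | Baseline/Screening Session | before visit |
| Random assignment | Intervention Phase | before visit |
| Written consent | Baseline/Screening Session; Section E | on arrival |
| In-person checks | same | after consent |
| First counselling | Appendix; COVID-19 modifications | Visit 1 |
| Pending review or medical clearance | Study 1 eligibility; Study 2 exclusions | can be after Visit 1 |

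Assignment therefore precedes consent, every in-person check and any later review.

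**2. Which exclusions could depend on the arm.** CO/NicAlert, breath alcohol, urine screen, pregnancy test, blood pressure, heart rate and the listed medications are thresholds or facts. Applied by staff unaware of the arm, they do not bias the comparison. Judgement enters mainly through the medical/psychiatric risk criterion and medical clearance.

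**3. Which factor is exposed.** The blinding sentence covers at least immediate versus gradual tapering. It cannot readily cover counsellors for targeted versus standard, because they deliver the counselling that differs.

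**4. The plan's power figure.** Inputs from Sample Size Determination: 104 per level, 20% versus 20% + 18 points = 38%, two-sided alpha .05. Pooled-variance normal approximation:

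Power = Φ{ [|p2 − p1| − 1.96·√(2p̄(1 − p̄)/n)] / √[(p1(1 − p1) + p2(1 − p2))/n] }, with p̄ = 0.29 and n = 104.

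- Null standard error: √(2 × 0.29 × 0.71 / 104) = 0.0629; times 1.96 = 0.1233.
- Alternative standard error: √((0.16 + 0.2356)/104) = 0.0617.
- (0.18 − 0.1233)/0.0617 = 0.92, so power = 0.82.

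The difference detectable at exactly 0.80 power is 17.5 points, in line with the stated approximate 18. The power statement reproduces.

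**5. What selective exclusion could do (assumed numbers).** Suppose there is no true effect and 20% are abstinent in both levels of 104. Suppose also that x extra would-be smokers are excluded from one level only. Its apparent rate becomes 20.8/(104 − x).

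| x (assumed) | Apparent rate | Shift | Type I error |
|---|---|---|---|
| 5 | 21.0% | 1.0 point | 5.4% |
| 10 | 22.1% | 2.1 points | 6.6% |
| 20 | 24.8% | 4.8 points | 12.4% |

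The documents give no x. For scale, x = 20 is 24% of the 83.2 smokers expected in a level (104 × 0.80).

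**6. Screening counts.** 0.80 × 300 = 240. 208/0.80 = 260. 208/300 = 69.3%. The Project Timeline note budgets 208 screening/baseline sessions, the same number as the eligible participants, so it leaves no screening visit for anyone who fails.

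**The case against.** The best defence is that the overview describes who makes up the 208, not a sequence, and that the assignment sentence may refer to a list or slot prepared before the visit and used only once a person qualifies. That may have been the practice, but the text says that participants are assigned and nowhere says that the assignment stays sealed. If it did stay sealed, one sentence settles the point.

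It is also fair that most exclusions are objective, that tapering is blinded, and that 5 or 10 selective exclusions would move type I error only to 5.4% or 6.6%. All of that stands and limits the weight of the point. So does timing: this is Version 12 of June 2021, and a change of order may reach few participants.

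Three stronger readings are tempting and not supported.

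- *The intent-to-treat set is open, and dismissed people might be counted as smoking.* Keeping all 260 or 300 on that rule would shrink the difference from 18.0 to 14.4 or 12.5 points. But the overview, Sample Size Determination and Section E all tie the RCT to 208, whom the overview calls eligible and randomised, and no section proposes keeping dismissed people as smokers.
- *The trial is underpowered because 208 is the number assigned before failures.* With an assumed 20% to 31% failing and dropped, power would be 0.73 to 0.67. That would remove about 42 to 64 people, whereas the Project Timeline note expects 198 at the first pre-quit week, a loss of 10.
- *People are treated without consent.* Consent precedes all data collection, and study cigarettes go only to those found eligible.

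**Conclusion.** The point holds as a fault in the stated order of steps and should be fixed. As written, allocation precedes consent and eligibility, and nothing in the documents hides the arm from those who decide eligibility. The possible harm is bias in the targeted-versus-standard comparison through discretionary exclusions. It depends on two things that the documents do not establish: that the deciders know the arm, and that exclusions differ by arm. Bias is possible, not shown, and its size is unknown; the illustration suggests that it is small unless exclusions differ clearly between arms. The planned power of about 0.80 is sound for 208 eligible participants. Confidence is high on the textual point and does not extend to any claim that the result is biased.

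**What to change.** **Assignment.** Change the Intervention Phase sentence so that the next concealed assignment is opened only after written consent, all eligibility checks and any pending PI, Co-I or medical determination, and before Visit 1 counselling. Where eligibility is pending, open it at the additional visit. State that those deciding eligibility cannot see the assignment. The intent-to-treat set is then simply the 208 so randomised.

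**If enrolment already followed the current text.** Report everyone assigned and every exclusion after assignment, by arm, with reason and timing.

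**Separately.** Correct the overview: 208 is 80% of 260 or 69% of 300, and 80% of 300 is 240. Reconcile it with the 208 screening/baseline sessions in the Project Timeline note.

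**Cost.** Text changes and restricted access to the list; no new visit type, measure or participants. All arms smoke the same normal-nicotine cigarettes in the baseline week, so nothing before Visit 1 counselling depends on the arm. The downside is practical: both sets of booklets must be ready at Visit 1, and first counselling is delayed for participants whose eligibility is pending.
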